### **5.5.2. Withdrawal Procedures**

In the event that the decision is made to permanently discontinue the study drug, the subject will be withdrawn from the study and the EOT visit should be conducted. Reasonable efforts should be made to have the subject return for a follow-up visit as described in Section 6. The last date of the last dose of study drug and the reason for subject withdrawal will be recorded in the eCRF.

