### **5.5. Withdrawal of Subjects From Study Treatment**

The decision to discontinue study treatment will not constitute study completion (see Section 5.5.3). In the event that the decision is made to discontinue study treatment, the treatment period will be considered complete, and the follow-up period will begin.

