**If a subject is withdrawn from study treatment:**

- The study monitor or sponsor must be notified.
- The reason(s) for withdrawal must be documented in the subject's medical record and in the eCRF.
- The EOT visit should be performed.
- The date of the EOT visit should be registered in the IVRS.
- Subjects must be followed for safety until the time of the follow-up visit or until study drug–related toxicities resolve, return to baseline, or are deemed irreversible, whichever is longest.

If the subject discontinues study treatment and actively withdraws consent for collection of follow-up data (safety follow-up or disease assessment), then no additional data collection should occur; however, subjects will have the option of withdrawing consent for study treatment but continuing in the follow-up period of the study for safety/efficacy assessments.

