### **6.5.2. Post-Treatment GVHD Follow-Up**

Subjects who completed study treatment or discontinued treatment for reasons other than GVHD progression will be followed every 28 days ( $\pm 7$  days) after the safety follow-up visit until any of the following occurs:

- GVHD progression.
- Initiation of a new anti-GVHD therapy.
- Relapse/recurrence of underlying hematologic disease.
- A maximum of 12 months from EOT or a maximum of 24 months from Day 1 is reached, whichever occurs first.

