### **6.5.3. Survival Follow-Up**

Subjects who complete post-treatment follow-up or experience GVHD progression or require a new anti-GVHD therapy should be contacted by telephone, email, or visit at least every 8 weeks ( $\pm 7$  days) to assess for new GVHD therapy and survival status until death, withdrawal of consent, or the end of the study, whichever occurs first.

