7.3.1. Primary Efficacy Analysis

7.3.1.1. Day 28 Overall Response Rate

The primary efficacy endpoint, ORR at Day 28 (ie, with either a CR, VGPR, or PR at Day 28 assessment or other response assessments within 3 days of Day 28, before start of new anti-GVHD therapy), will be analyzed using a stratified CMH test. Note that the EOT visit must be accounted for in the Day 28 ORR calculation, because when the EOT and Day 28 visits occur at the same time, per protocol, EOT will supersede the Day 28 visit. That is, if the EOT visit occurs when the Day 28 visit is planned, data from the EOT visit will be used in lieu of the Day 28 visit.

Responders ([CIBMTR 2009](#), [Harris et al 2016](#); refer to Protocol Appendix B):

- (CR) Complete response
- (VGPR) Very good partial response
- (PR) Partial response

Non-responders:

- (MR) Mixed response
- (PD) Progression of disease
- (NR) No response
- (NA) Not applicable
- Other
- Missing (primary reason)
 - Death prior to the Day 28 visit
 - Withdrawal from study prior to the Day 28 visit
 - Initiation of new anti-GVHD therapy prior to the Day 28 visit
 - Missing visit

Day 28 ORR will be summarized using descriptive statistics (N, %) by treatment group with 2-sided exact binomial 95% CIs. P-value, mean proportion difference, odds ratio, and 95% Wald confidence limits calculated from stratified CMH test will be also presented.

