7.4. Analysis of the Secondary Efficacy Endpoints

7.4.1. Key Secondary Endpoint Analysis

Nonrelapse mortality is defined as death due to causes other than malignancy relapse. For the primary analysis, the NRM rate will be estimated using the proportion of subjects with a death due to causes other than malignancy relapse within the subjects who were known alive at Day 180 or who had such a death. Reasons for not including a subject in this proportion include:

- Subject was alive and had not reached Day 180
- Death due to malignancy relapse
- Subject ended study participation prior to Day 180 (summarized by reason for study withdrawal)

A sensitivity analysis will also be conducted estimating the NRM rate using the KM estimator for each treatment.

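### Protocol 5.5.2 withdraws from the study anyone who permanently stops study drug, against the rest of the protocol; read literally, it would remove subjects informatively from the Month 6 NRM analysis

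*Protocol*

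**What the plan says.** **The instruction at issue.** Protocol 5.5.2 states that on permanent discontinuation of study drug "the subject will be withdrawn from the study and the EOT visit should be conducted". It then asks for reasonable efforts to obtain a follow-up visit.

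**Text pointing the other way.**
- Protocol 5.5: "The decision to discontinue study treatment will not constitute study completion", and on stopping, "the treatment period will be considered complete, and the follow-up period will begin".
- Protocol 4.4 and 4.5: a subject who stops treatment enters follow-up, and all subjects are followed for survival until death, withdrawn consent or study end.
- The list that completes 5.5.2: data collection ends only if consent to follow-up is actively withdrawn. Subjects may stop treatment while "continuing in the follow-up period of the study for safety/efficacy assessments".
- Protocol 6.5.2: those who "discontinued treatment for reasons other than GVHD progression will be followed every 28 days".
- Protocol 6.5.3: those who "experience GVHD progression or require a new anti-GVHD therapy should be contacted by telephone, email, or visit at least every 8 weeks".

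**How the SAP uses study withdrawal.** SAP 7.4.1 estimates NRM among subjects known alive at Day 180 or with a non-relapse death. Its listed reasons for exclusion include "Subject ended study participation prior to Day 180". SAP 7.4.1.1 repeats the exclusion for subjects who withdrew before Day 180, without mentioning those whose non-relapse death is known. The Kaplan-Meier sensitivity analysis (SAP 7.4.1.2) censors subjects without a non-relapse death at study withdrawal, relapse death or last contact, whichever is earliest.

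**The concern.** Section 5.5.2 is the procedure a site turns to when drug stops, so its wording can decide how disposition is recorded. The SAP then acts on that record. Under Protocol 5.5.1, mandatory reasons to stop include unacceptable toxicity and the need for additional systemic therapy because of GVHD progression or lack of response. Protocol 1.4.3 regards Day 28 response as prognostic for 6-month NRM. The subjects at issue are therefore unlikely to be a random subset, and if the drug works there should be more of them on placebo. NRM at Month 6 is the only endpoint besides Day 28 ORR under type I error control. The 5% allowance in Protocol 9.2 covers only subjects with no response data before Day 28, not later losses.

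**Working it through.** **1. The plan's own figure.** Protocol 9.2 states 83% power for NRM: 207 per arm, strata 50:50, 22% vs 12.4% and 44% vs 28.2%, one-sided 0.025, CMH test. Each stratum has 103.5 per arm, so its weight is 103.5/2 = 51.75.
- Numerator: 51.75 × (0.096 + 0.158) = 13.14; less 0.5 for continuity, 12.64.
- Null SD: √[51.75 × (0.172×0.828 + 0.361×0.639)] = 4.394.
- Alternative SD: √[25.875 × (0.1716 + 0.1086 + 0.2464 + 0.2025)] = 4.343.
- Power: Φ[(12.64 − 1.96×4.394)/4.343] = Φ(0.928) = 82.3%, which reproduces 83%.

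The scenarios below use a pooled two-proportion formula without continuity correction, which handles unequal arms. With no loss it gives 86.4%, so compare them with 86.4%, not 83%.

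**2. Who is affected.** Only subjects who stop before Day 180. Those who stop later were known alive at Day 180 and stay in.

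**3. Non-informative loss.** Losing 10%, 20%, 30% or 40% of each arm gives power of 82.7%, 78.0%, 72.4% or 65.7%.

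**4. Informative loss, later deaths not recorded.** The documents give no rate of stopping before Day 180. As an assumption, take the planned Day 28 nonresponders as the group that stops: 1 − 0.56 = 44% placebo, 1 − 0.72 = 28% itacitinib. Let nonresponders have r times the responders' NRM and hold each arm's overall rate at 33% or 19.8%. Responder NRM is then p / [(1 − f) + f·r], with p the arm's NRM and f its nonresponder share.

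For r = 2 with all nonresponders leaving:
- Placebo: 0.33/(0.56 + 0.88) = 22.9%, n = 207×0.56 ≈ 116.
- Itacitinib: 0.198/(0.72 + 0.56) = 15.5%, n = 207×0.72 ≈ 149.
- Difference 7.4 points; pooled SE 0.0483, unpooled SE 0.0490.
- Power: Φ[(0.0745 − 1.96×0.0483)/0.0490] = Φ(−0.41) = 34%.

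| Nonresponders leaving | r | n (placebo, itacitinib) | Observed NRM | Difference (points) | Power |
|---|---|---|---|---|---|
| All | 1 | 116, 149 | 33.0% vs 19.8% | 13.2 | 68% |
| All | 2 | 116, 149 | 22.9% vs 15.5% | 7.4 | 34% |
| All | 3 | 116, 149 | 17.6% vs 12.7% | 4.9 | 20% |
| Half | 1 | 161, 178 | 33.0% vs 19.8% | 13.2 | 79% |
| Half | 2 | 161, 178 | 29.4% vs 18.0% | 11.4 | 70% |
| Half | 3 | 161, 178 | 27.5% vs 16.8% | 10.6 | 66% |

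SAP 3.4.2 tests NRM at 0.0125. At that level the two r = 2 powers become 25% (all) and 59% (half), against 79% with no loss.

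**5. Informative loss, deaths recorded and survivors dropped.** With r = 2 and all nonresponders leaving, nonresponder NRM is 45.8% on placebo and 30.9% on itacitinib.
- Placebo: 0.33/(0.56 + 0.44×0.458) = 43.3%.
- Itacitinib: 0.198/(0.72 + 0.28×0.309) = 24.5%.

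Both rates are overstated, and the difference grows to 18.8 points. The direction of bias turns on which deaths are captured, the point on which SAP 7.4.1 and 7.4.1.1 do not agree.

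**The case against.** The strongest reply is that no careful site would read 5.5.2 this way. It sits under a heading about withdrawal from study treatment. Its next sentence asks for a follow-up visit, and its own list ends data collection only on withdrawn consent. Section 4.5 promises survival follow-up for everyone, and 6.5.3 names the treatment failures explicitly. SAP 6.2 counts treatment discontinuation and study withdrawal separately. This stands: the sentence is probably a drafting slip, and its effect depends on site practice. It does not make the sentence harmless, since it is an operative instruction and the SAP excludes on the status it assigns.

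A reader might also infer more than the documents support:
- **That 44% and 28% of subjects would be lost, with most of their deaths.** Protocol 5.5.1 requires stopping when additional therapy is needed, which is not the same as Day 28 nonresponse. SAP nonresponders also include early deaths and missed visits.
- **That the bias runs one way.** SAP 7.4.1 keeps subjects with a known non-relapse death, and SAP 7.4.1.2 censors only those without one.
- **That overall survival is cut short.** SAP 7.4.10 censors only subjects without an observed death, at the later of withdrawal or last contact.
- **That Day 28 ORR is distorted.** SAP 7.3.1.1 does list "Withdrawal from study prior to the Day 28 visit" as nonresponse, but new anti-GVHD therapy or a missing visit before Day 28 already has that result.

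**Conclusion.** The contradiction is real and should be corrected. Its consequence is conditional: if 5.5.2 were applied literally, subjects stopping drug before Day 180 would leave the primary NRM analysis informatively and possibly unequally by arm. The Kaplan-Meier sensitivity analysis would not repair this for deaths that went unrecorded after withdrawal. The fall from 13.2 to about 7.4 points, with 34% power, assumes that every planned Day 28 nonresponder leaves, that none of their deaths is recorded, and that they carry twice the responders' NRM. It is an illustration, not an estimate. Nothing in the documents shows that sites followed 5.5.2 literally.

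**What to change.** 1. **Protocol 5.5.2.** Say that the subject is withdrawn from study treatment and enters follow-up under Section 6.5, in line with 4.5 and 5.5. Reserve study withdrawal for withdrawn consent to follow-up or loss to follow-up. This is one sentence and changes no dose or treatment-stopping rule.
2. **SAP 7.4.1 and 7.4.1.1.** State in both, in the same terms, whether a non-relapse death known to have occurred by Day 180 counts after study withdrawal. This is one clause.
3. **Existing records.** The Interim Analysis 2 cutoff predates SAP Amendment 1, so new wording alone does not correct entries already made. A blinded listing of subjects whose study withdrawal coincides with end of treatment, without withdrawn consent, loss or death, would show whether any were misclassified.

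With these changes, stopping drug alone no longer removes a subject, and the planned 207 per arm is not eroded by this route. The SAP would still exclude relapse deaths and genuine withdrawals or losses.

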**If a subject is withdrawn from study treatment:**

- The study monitor or sponsor must be notified.
- The reason(s) for withdrawal must be documented in the subject's medical record and in the eCRF.
- The EOT visit should be performed.
- The date of the EOT visit should be registered in the IVRS.
- Subjects must be followed for safety until the time of the follow-up visit or until study drug–related toxicities resolve, return to baseline, or are deemed irreversible, whichever is longest.

If the subject discontinues study treatment and actively withdraws consent for collection of follow-up data (safety follow-up or disease assessment), then no additional data collection should occur; however, subjects will have the option of withdrawing consent for study treatment but continuing in the follow-up period of the study for safety/efficacy assessments.

### **5.5.3. Study Completion**

A subject will be considered as completing the study if they meet any of the following criteria:

- Subject dies and a date of death is available.
- Subject is known to have died; however, the date of death cannot be obtained. (NOTE: Every effort must be made to obtain the date of death.)
- Subject has discontinued study treatment and has withdrawn consent for collection of follow-up anticancer and survival data.

#### **5.5.4. Concomitant Medications**

##### **5.5.4.1. Permitted Medications**

Concomitant treatments and/or procedures that are required to manage a subject's medical condition (including prophylactic and/or supportive care medications as described in Section 5.2.3) during the study will also be recorded in the eCRF.

##### **5.5.4.2. Restricted Medications**

The following medications have restrictions on use during the treatment period of the study:

- Aspirin in doses exceeding 125 mg per day is not permitted. Low-dose aspirin ( $\leq 125$  mg per day) is permitted unless clinically contraindicated.
- Coadministration with the following potent CYP3A4 inhibitors: itraconazole, voriconazole, mibefradil, and clarithromycin; if the subject's medical condition requires treatment with any of these drugs, dose reduction of itacitinib to 100 mg QD is recommended, as more potent inhibitors have been shown to increase exposure to itacitinib. The sponsor's medical monitor may be consulted for advice when using these agents.

No dose adjustment is recommended for concomitant administration of other CYP3A4 inhibitors ([Appendix D](#)).

- Coadministration with CYP3A4 inducers ([Appendix D](#)).
- If concomitant administration of an anticoagulant/antiplatelet medication is indicated, then caution and enhanced monitoring is required. History of thrombocytopenia should be a factor in the choice of anticoagulant and dose.

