In a healthy volunteer study, coadministration of 200 mg itacitinib with 200 mg QD of itraconazole resulted in a nearly 5-fold increase in exposure. A PBPK model was used to simulate a 100 mg QD itacitinib dose when coadministered with itraconazole. The resulting exposure (2306 nM·h) approximates that observed in GVHD patients taking 300 mg QD alone (2855 nM·h). Therefore, it is recommended that subjects taking the following potent CYP3A4 inhibitors have a dose reduction of itacitinib to 100 mg QD (from 200 mg or 300 mg QD): itraconazole, voriconazole, mibefradil, and clarithromycin. No dose adjustment is recommended for concomitant administration of other CYP3A4 inhibitors.

The study population is composed of patients with various hematologic diseases and expected to be heterogeneous for individual primary disease and allo-HSCT characteristics. Exploratory and/or sensitivity subgroup analyses will be performed as described in Section 9.4.

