#### **5.2.4. Prophylactic and Supportive Care Medications**

Patients who undergo allo-HSCT are at risk for a variety of infections based on the degree of immunosuppression induced by the conditioning regimen before transplant. As such, it is considered routine practice to use antibiotics, anti-infectives, and immunizations as prophylactic therapies ([Tomblyn et al 2009](#)). In cases where post-transplant anti-infective prophylaxis measures are necessary, ongoing therapy may continue at the investigator's discretion per institutional guidelines.

Systemic and topical GVHD prophylaxis medications (eg, cyclosporine, methotrexate, and tacrolimus) may be continued at therapeutic doses as appropriate based on stage and sites of disease.

Additional supportive care measures (eg, use of antimotility agents for diarrhea management, topical steroids, beclomethasone, budesonide, ursodiol) are permitted at the investigator's discretion.

See Section [5.5.4](#) for additional details.

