***In Vivo* CYP3A Inhibitors**

Inhibitor	Therapeutic Class	Inhibitor dosing (oral)	Object  (oral, unless otherwise specified)	AUC ratio	PMID or NDA #	Published
Potent CYP3A Inhibitors (yielding substrate AUCr > 5)						
VIEKIRA PAK 	Antivirals	See note 	tacrolimus 	55.76	25708713	2015 May
indinavir /RIT	Protease Inhibitors	800/100 mg BID (1 day)	alfentanil	36.5	19225389	2009 Mar
tipranavir/RIT	Protease Inhibitors	500/200 mg BID (2 days)	midazolam	26.91	20147896	2010 Jun
ritonavir	Protease Inhibitors	3 doses of 100 mg over 24 h	midazolam	26.41	20002087	2009 Dec
cobicistat (GS-9350)	None	200 mg QD (14 days)	midazolam	19.03	20043009	2010 Mar
indinavir	Protease Inhibitors	800 mg TID (7 days)	varafenafil	16.25	NDA # 021400	2003 Aug
ketoconazole	Antifungals	400 mg QD (4 days)	midazolam	15.9	8181191	1994 May
troleandomycin	Antibiotics	500 mg single dose	midazolam	14.8	15536460	2004 Dec
telaprevir	Antivirals	750 mg TID (16 days)	midazolam	13.5	22162542	2012 Oct
danoprevir / RIT	Antivirals	200/100 mg QD (14 days)	midazolam	13.42	23872824	2013 Nov
elvitegravir / RIT	Treatments of AIDS	150/100 mg QD (10 days)	midazolam	12.8	NDA # 203100	2012
saquinavir / RIT	Protease Inhibitors	1000/100 mg BID (14 days)	midazolam	12.48	19792991	2009 Oct
lopinavir / RIT	Protease Inhibitors	400/100 mg BID (2 days)	alfentanil	11.47	24067429	2013 Dec
itraconazole	Antifungals	200 mg QD (4 days)	midazolam	10.8	8181191	1994 May
voriconazole	Antifungals	200 mg BID (9 days)	midazolam	9.63	21937987	2011 Nov
mibefradil	Calcium Channel Blockers	100 mg single dose	midazolam	8.86	14517191	2003 Oct
LCL161	Cancer Treatments	600 mg single dose	midazolam	8.8	23585187	2013 Jun
clarithromycin	Antibiotics	500 mg BID (7 days)	midazolam	8.39	16432272	2006 Feb
posaconazole	Antifungals	400 mg BID (7 days)	midazolam	6.23	19302901	2009 Feb
telithromycin	Antibiotics	800 mg QD (6 days)	midazolam	6.2	NDA# 021144	2004
grapefruit juice Ds 	Food Products	240 mL TID (2 days) and 90 min, 60 min, 30 min prior to midazolam	midazolam	5.95	12953340	2003 Aug
conivaptan	Diuretics	40 mg BID (5 days)	midazolam	5.76	NDA # 021697	2005
nefazodone	Antidepressants	100-200 mg BID (12 days)	midazolam	5.44	14551182	2003 Nov
nelfinavir	Protease Inhibitors	1250 mg BID (14 days)	midazolam	5.29	21406602	2011 Jun
saquinavir	Protease Inhibitors	1200 mg TID (5 days)	midazolam	5.18	10430107	1999 Jul

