 To allow better comparability, DDI studies with the probe substrate midazolam were selected first.  
When no study with midazolam was available, the AUCratio of another probe or sensitive substrate is presented.

 VIEKIRA PAK = 150/100 mg paritaprevir/ritonavir + 25 mg ombitasvir + 800 mg dasabuvir for 28 days. Tacrolimus is also a substrate of OATP1B1/1B3 that can be inhibited by Viekira Pak.

 240 mL GFJ double-strength administered TID for 3 days

 Of note, co-administration of ciprofloxacin (750 mg BID for 7 days) did not affect plasma concentrations of ivacaftor, which is also a sensitive substrate for CYP3A (KALYDECO Prescribing Information).

 Fostamatinib also inhibits BCRP, and BCRP inhibition likely participates to the increase in exposure of simvastatin

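### Sections 1.5 and 5.5.4.2 leave ketoconazole at itacitinib 200 mg although Protocol Appendix D and the SAP rank it above the inhibitors that trigger 100 mg; troleandomycin is in the same position on weaker evidence

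*Protocol*

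**What the plan says.** Protocol Section 5.5.4.2 names four potent CYP3A4 inhibitors: itraconazole, voriconazole, mibefradil and clarithromycin. With any of them it recommends lowering itacitinib from the 200 mg starting dose to 100 mg QD, "as more potent inhibitors have been shown to increase exposure to itacitinib". The next sentence covers all the rest and points to Appendix D: "No dose adjustment is recommended for concomitant administration of other CYP3A4 inhibitors". Section 1.5 gives the same two recommendations.

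Section 1.5 also gives the itacitinib data behind the rule. In healthy volunteers, "coadministration of 200 mg itacitinib with 200 mg QD of itraconazole resulted in a nearly 5-fold increase in exposure". A pharmacokinetic model then put 100 mg QD with itraconazole at 2306 nM·h, an exposure that "approximates that observed in GVHD patients taking 300 mg QD alone" (2855 nM·h).

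Protocol Appendix D lists CYP3A inhibitors by the AUC ratio they produce in a probe substrate. Its first footnote says "To allow better comparability, DDI studies with the probe substrate midazolam were selected first". Separately, SAP 8.2.2 classifies azole use for adverse-event tables in a strongest-to-weakest order that runs ketoconazole, itraconazole, voriconazole, posaconazole, fluconazole.

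**The concern.** The reason given for the reduction is potency, but the rule works from a closed list. Two drugs that the protocol's own table ranks above every name on that list fall under the no-adjustment sentence. A site following the text would halve the dose with itraconazole and keep the full dose with ketoconazole.

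Nothing in the plan stops this before exposure occurs. Section 5.5.4.3 prohibits neither drug. The offer of medical-monitor advice in Section 5.5.4.2 attaches to the four named agents. Section 5.2.4 notes that after transplant "it is considered routine practice to use antibiotics, anti-infectives, and immunizations as prophylactic therapies", so anti-infective use is expected in general. That shows the drugs are allowed, not that they are taken.

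What is at stake is avoidable over-exposure in individual subjects, which could arise only on the itacitinib arm. For contrast, Section 3.3.1 asks subjects to avoid grapefruit juice because of CYP3A inhibition. Protocol Appendix D lists grapefruit juice at 2.39, or 5.95 for the double-strength regimen.

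**Working it through.** The plan states no figure that could be reproduced here. The check compares the dosing list with the protocol's ranking and then illustrates what an unreduced dose could mean.

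**1. Ranking (Protocol Appendix D, AUC ratio with midazolam)**

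| Drug | Ratio | Dose recommended with it |
|---|---|---|
| Ketoconazole | 15.9 | 200 mg (no adjustment) |
| Troleandomycin | 14.8 | 200 mg (no adjustment) |
| Itraconazole | 10.8 | 100 mg |
| Voriconazole | 9.63 | 100 mg |
| Mibefradil | 8.86 | 100 mg |
| Clarithromycin | 8.39 | 100 mg |
| Posaconazole | 6.23 | 200 mg (no adjustment) |

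Relative to itraconazole: ketoconazole 15.9/10.8 = 1.47; troleandomycin 14.8/10.8 = 1.37.

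**2. How comparable the rows are.** Ketoconazole and itraconazole share a source number (8181191), the same probe and a 4-day once-daily regimen. SAP 8.2.2 puts them in the same order. Troleandomycin comes from another source, was given as a "500 mg single dose", and does not appear in the SAP order. Its rank is therefore less secure.

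**3. How many entries are affected.** The potent category (ratio above 5) has 27 entries, of which 18 are at or above clarithromycin.
- Unnamed: 18 − 4 = 14.
- Of these, 11 are HIV or HCV antivirals or boosters, which the HIV and active-hepatitis exclusions in Section 3.2 make unlikely, and 1 is a cancer agent (LCL161, 8.8).
- Remaining: 14 − 11 − 1 = 2, namely ketoconazole and troleandomycin. The other unnamed entries number 12.

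**4. Does the midazolam scale carry over to itacitinib?** Not directly. Itraconazole gives 10.8 with midazolam and nearly 5-fold with itacitinib: about 5/10.8 = 0.46. The table supports an order of strength, not an exposure estimate.

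**5. Illustration of an unreduced 200 mg dose.** Assume an inhibitor of itraconazole strength and start from 2306 nM·h at 100 mg.
- If exposure is dose-proportional: 2 × 2306 = 4612 nM·h, and 4612/2855 = 1.62 times the exposure on 300 mg alone.
- If doubling the dose added nothing: 2306 nM·h, and 2306/2855 = 0.81 times.

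The range spans the 300 mg exposure. It is not specific to ketoconazole or troleandomycin, and the 300 mg exposure is the protocol's comparator, not a stated safety limit.

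**The case against.** The strongest reply is that neither section says the four drugs were picked by midazolam rank. The stated reason concerns itacitinib exposure. Item 5 of the Amendment 4 summary in Protocol Appendix E ties the CYP3A4 recommendation to emerging data from INCB 39110-108 added to Section 1.5, and a redacted block stands just before the itraconazole paragraph there. The sponsor may hold itacitinib data that justify the list. This stands. A reader might infer that the rule contradicts its own rationale or has no basis; the documents do not support going that far, because the basis may lie in text that cannot be seen.

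A second reply is that safeguards exist. Both sentences are recommendations. Section 5.4.2 leaves room for clinical judgement on individual dose reductions, Table 1 handles neutrophil and platelet falls, Section 7.7.1 provides predose samples on Days 7 and 28 (fuller sampling in the first 112 subjects), Section 9.4.5 allows simulation of dose changes for covariates that affect exposure, and SAP 8.2.2 tabulates adverse events by azole use. All true, but each acts after exposure or toxicity.

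A third reply is that no affected subject is shown and that change comes late: SAP Appendix D tabulates Interim 2 sets of 410 to 435 out of 436. This limits the benefit without removing it. Subjects still on study continue treatment after the primary analysis (Section 4.5), and re-treatment uses open-label itacitinib (Section 6.4).

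**Conclusion.** The point holds and is minor. As written, the recommendation keeps ketoconazole at 200 mg while Protocol Appendix D and SAP 8.2.2 both rank it above itraconazole, which triggers 100 mg. The case for troleandomycin has the same form on weaker evidence.

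The conclusion assumes that the order of potency seen with midazolam is at least a rough guide for itacitinib, and that no redacted data justify the exemption. The number of subjects affected is unknown and may be zero.

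Three stronger readings should be resisted:
- That subjects on ketoconazole would reach about 4600 nM·h. That figure assumes itraconazole strength and dose proportionality, and the alternative assumption gives less than the 300 mg exposure.
- That posaconazole or other lower-ranked inhibitors should also trigger a reduction. They rank below every named drug, so this argument does not reach them.
- That the trial's inference is affected. Nothing here bears on the primary endpoint, alpha or power.

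**What to change.** In both Section 1.5 and Section 5.5.4.2:
- Add ketoconazole to the 100 mg QD list.
- Add troleandomycin to the list, or refer it to the medical monitor.
- Limit the no-adjustment sentence to inhibitors that Protocol Appendix D ranks below the named drugs. Posaconazole then stays unadjusted.
- Refer the other 12 unnamed entries ranked above clarithromycin to the medical monitor.

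If itacitinib-specific data support 200 mg with ketoconazole, one sentence saying so would settle the point instead.

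The cost is an amendment to the wording of two sections, with sponsor and then IRB/IEC approval (Section 10.1), across about 85 sites (Section 4.3.1). It needs no new visits, procedures or samples, and could be folded into the next amendment. The clinical downside is that a few subjects would start at 100 mg, from which the next step is discontinuation (Section 5.4.2, Table 2). They could be underdosed if midazolam potency does not carry over to itacitinib.
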